9.4. Variables

Adherence study

After confirmation of eligibility criteria, investigators will collect the following data for each subject selected, based on clinical/pharmacy/prescription records. Each selected subject may have one or more valid patient-regimens. Data on all valid patient-regimens should be collected. A valid patient-regimen is defined in the Inclusion Criteria Section.

Demographics	 Subject initials (where permissible) Date of birth (where permissible) Gender (male, female, transgender) Race (White, Asian, Black or African heritage, other)
Baseline characteristics	 Most likely mode of HIV infection (injection drug user, heterosexual sex, homosexual sex, unknown, other) Date of ART initiation Number of virological failures (HIV RNA >50 copies/mL in two consecutive measures after HIV RNA <50 copies/mL has been achieved in that regimen) as of January 1st 2009 HIV RNA (copies /mL) at ART initiation CD4 count at ART initiation and CD4 nadir (if available)
Patient-regimen characteristics (characteristics to be evaluated at each	 Illegal drugs dependency with current consumption Alcohol dependency with current consumption

 Table 2.
 Adherence study– Variables to be collected

1.1	
valid regimen initiation) Note: For the purpose of evaluating these characteristics; if the regimen started after January 1 st 2009, the day of initiation should be considered and if the regimen started before January 1 st 2009, January 1 st 2009 should be considered	 Smoker with current consumption Current opioid substitution treatment (use of methadone, buprenorphine or buprenorphine/naloxone) Mental disorder (present, controlled or uncontrolled) AIDS status Hepatitis C Charlson comorbidity Index
Antiretroviral treatment prescription (for each valid patient-regimen)	 For each drug/co-formulation: scientific / generic name (which includes active principles, dosages and number of pills per day) Date of discontinuation, if available
Laboratory parameters (all CD4 and HIV RNA tests performed during the observation period)	For each test: - Date of test - corresponding value
Resistance profile (all tests performed during the observation period)	 For each test: Date of test Was the REGA 8.0 algorithm used? Genotype Sensitivity Score (Susceptive, intermediate or resistant) for each drug
Inpatient care (all episodes performed in the observation period)	 For each episode: Date of admission Admission diagnosis Date of discharge Destination at discharge Event code (DRG) ICD-9 or ICD-10 code (primary and secondary) Total cost of hospitalisation, including medications
Antiretroviral treatment pharmacy refills (for each valid patient-regimen)	 For each drug of each regimen: Date of refill (dd/mm/yyyy) scientific / generic name (which includes active principles, dosages, pharmaceutical forms), Quantity dispensed
Adverse Drug Reactions	 For each episode Adverse Drug Reaction description Seriousness Start and End dates or ongoing Relation to Gilead drug
Pregnancy (if applicable)	 Last menstrual period Date of pregnancy confirmation Estimated date of delivery or outcome if available at the time of the review

Prescription errors sub-study

After confirmation of eligibility criteria, investigators will collect the following data for each hospitalization episode selected, based on clinical/pharmacy/prescription records:

Individual characteristics (at the beginning of each hospitalization enigode)	- Subject initials (where permissible)
	- Date of birth
episode)	- Gender (male, female, transgender)
	- Race (White, Asian, Black or African heritage, other)
	- Non ART concomitant medications
Inpatient care (for each hospitalization	- Date of admission
episode)	- Admission diagnosis
	- Date of discharge
	- Discharge diagnosis
	- Destination at discharge
	- ICD-9 or ICD-10 code (primary and secondary)
	- DRG code Admitting service: HIV/AIDS, Medicine, Surgery, Obstetrics and Gynaecology, Neurology / Psychiatry, Other
	- Degree of the prescribing physician: Assistant / Junior doctor, Graduated Assistant / Registrar, Senior Graduated Assistant / Consultant, Other
	- Transferred within the first 48 hours? If so where to and when?
	- ART prescribed in the first 48 hours: active substances, dosage of each, scheduling
Prescription errors audit (for each error)	- Type of error:
Prescription errors audit (for each error)	 Type of error: (1) absence / incomplete regimen
Prescription errors audit (for each error)	 Type of error: (1) absence / incomplete regimen (2) incorrect dosage [including renal dose adjustment]
Prescription errors audit (for each error)	 Type of error: (1) absence / incomplete regimen (2) incorrect dosage [including renal dose adjustment] (3) incorrect schedule
Prescription errors audit (for each error)	 Type of error: (1) absence / incomplete regimen (2) incorrect dosage [including renal dose adjustment] (3) incorrect schedule (4) incorrect formulation
Prescription errors audit (for each error)	 Type of error: (1) absence / incomplete regimen (2) incorrect dosage [including renal dose adjustment] (3) incorrect schedule (4) incorrect formulation (5) duplication of ART therapy
Prescription errors audit (for each error)	 Type of error: (1) absence / incomplete regimen (2) incorrect dosage [including renal dose adjustment] (3) incorrect schedule (4) incorrect formulation (5) duplication of ART therapy (6) non-recommended drug-drug combinations (ART-ART and ART-non-ART)
Prescription errors audit (for each error)	 Type of error: (1) absence / incomplete regimen (2) incorrect dosage [including renal dose adjustment] (3) incorrect schedule (4) incorrect formulation (5) duplication of ART therapy (6) non-recommended drug-drug combinations (ART-ART and ART-non-ART) Drug-drug interactions will be evaluated according to the HIV drug-drug interaction website and are shown in red as contra-indicated;
Prescription errors audit (for each error)	 Type of error: (1) absence / incomplete regimen (2) incorrect dosage [including renal dose adjustment] (3) incorrect schedule (4) incorrect formulation (5) duplication of ART therapy (6) non-recommended drug-drug combinations (ART-ART and ART-non-ART) Drug-drug interactions will be evaluated according to the HIV drug-drug interaction website and are shown in red as contra-indicated; (www.hiv-druginteractions.org/Interactions.aspx)
Prescription errors audit (for each error)	 Type of error: (1) absence / incomplete regimen (2) incorrect dosage [including renal dose adjustment] (3) incorrect schedule (4) incorrect formulation (5) duplication of ART therapy (6) non-recommended drug-drug combinations (ART-ART and ART-non-ART) Drug-drug interactions will be evaluated according to the HIV drug-drug interaction website and are shown in red as contra-indicated; (www.hiv-druginteractions.org/Interactions.aspx) Was the error resolved?
Prescription errors audit (for each error) Adverse Drug Reactions	 Type of error: (1) absence / incomplete regimen (2) incorrect dosage [including renal dose adjustment] (3) incorrect schedule (4) incorrect formulation (5) duplication of ART therapy (6) non-recommended drug-drug combinations (ART-ART and ART-non-ART) Drug-drug interactions will be evaluated according to the HIV drug-drug interaction website and are shown in red as contra-indicated; (www.hiv-druginteractions.org/Interactions.aspx) Was the error resolved?
Prescription errors audit (for each error) Adverse Drug Reactions	 Type of error: (1) absence / incomplete regimen (2) incorrect dosage [including renal dose adjustment] (3) incorrect schedule (4) incorrect formulation (5) duplication of ART therapy (6) non-recommended drug-drug combinations (ART-ART and ART-non-ART) Drug-drug interactions will be evaluated according to the HIV drug-drug interaction website and are shown in red as contra-indicated; (www.hiv-druginteractions.org/Interactions.aspx) Was the error resolved? For each episode Adverse Drug Reactions description
Prescription errors audit (for each error) Adverse Drug Reactions	 Type of error: (1) absence / incomplete regimen (2) incorrect dosage [including renal dose adjustment] (3) incorrect schedule (4) incorrect formulation (5) duplication of ART therapy (6) non-recommended drug-drug combinations (ART-ART and ART-non-ART) Drug-drug interactions will be evaluated according to the HIV drug-drug interaction website and are shown in red as contra-indicated; (www.hiv-druginteractions.org/Interactions.aspx) Was the error resolved? For each episode Adverse Drug Reactions description Seriousness
Prescription errors audit (for each error) Adverse Drug Reactions	 Type of error: (1) absence / incomplete regimen (2) incorrect dosage [including renal dose adjustment] (3) incorrect schedule (4) incorrect formulation (5) duplication of ART therapy (6) non-recommended drug-drug combinations (ART-ART and ART-non-ART) Drug-drug interactions will be evaluated according to the HIV drug-drug interaction website and are shown in red as contra-indicated; (www.hiv-druginteractions.org/Interactions.aspx) Was the error resolved? For each episode Adverse Drug Reactions description Seriousness Start and End dates or ongoing
Prescription errors audit (for each error) Adverse Drug Reactions	 Type of error: (1) absence / incomplete regimen (2) incorrect dosage [including renal dose adjustment] (3) incorrect schedule (4) incorrect formulation (5) duplication of ART therapy (6) non-recommended drug-drug combinations (ART-ART and ART-non-ART) Drug-drug interactions will be evaluated according to the HIV drug-drug interaction website and are shown in red as contra-indicated; (www.hiv-druginteractions.org/Interactions.aspx) Was the error resolved? For each episode Adverse Drug Reactions description Seriousness Start and End dates or ongoing Relation to Gilead drug
Prescription errors audit (for each error) Adverse Drug Reactions Pregnancy (if applicable)	 Type of error: (1) absence / incomplete regimen (2) incorrect dosage [including renal dose adjustment] (3) incorrect schedule (4) incorrect formulation (5) duplication of ART therapy (6) non-recommended drug-drug combinations (ART-ART and ART-non-ART) Drug-drug interactions will be evaluated according to the HIV drug-drug interaction website and are shown in red as contra-indicated; (www.hiv-druginteractions.org/Interactions.aspx) Was the error resolved? For each episode Adverse Drug Reactions description Seriousness Start and End dates or ongoing Relation to Gilead drug Last menstrual period

Table 3.Prescription errors sub-study- variables to be collected

- Estimated date of delivery or outcome if available at the time of the review

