	• Confounder adjusted actual (i.e. OIA adjusted) monthly ART plus hospitalization costs by patient-regimens adherence level (NA and OIA)	
	• Proportion of hospitalization episodes with ART prescription errors overall and in STR versus non-STR groups	
	• Percentage of prescription errors, overall and STR versus non- STR.	
	The list of confounders to be included is detailed in the variables to be collected section. All variables collected will be considered as confounders except the dependent or related dependent variable in question for each endpoint.	
Data Sources:	Centers participating in the Adherence study must have the complete history (within the observation period) of pharmacy refills available electronically in the hospital records. Subjects' clinical records will be the main source for the remaining data to be collected.	
	For centers participating in the Prescription errors sub-study, registration of ART errors, in either paper or electronic format, is required. The main source of data is thus the subject clinical record.	
Study Size:	Adherence study	
	700 STR subjects and 805 non-STR subjects is the sample size needed to enable a final sample size for analysis of 2060 patient-regimens (assuming an average of 1.5 patient-regimens per subject), after matching on a variable ratio with a propensity score approach. This is necessary to achieve a power of 80% for detecting a difference of 0.02 in the proportion of subjects with adherence > 90% between the two cohorts, with a two sided test with a significance level of 0.05, determined using the methodology proposed by Sahai and Khurshid {27760}.	
	Prescription errors sub-study	
	Due to the nature of the study design a formal size determination could not be performed. Each center will aim to include 40 inpatient care episodes of HIV-1 infected subjects that occurred between 1st	

	January 2012 and 29th December 2013. There is no minimum number of subjects required since the unit of observation is the hospitalization episode. The subjects enrolled onto the sub-study do not need to be participating in the adherence study in order to be eligible.	
Data Analysis:	Baseline characteristics will be reported using descriptive statistics. In general, when presenting descriptive statistics, the following parameters will be presented:	

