	• for qualitative data: absolute and relative frequencies. Proportions, and 95% confidence intervals for parameters of interest, will be based on the total number of subjects with non-missing values unless specified otherwise. Counts for missing values will be also tabulated but missing values will not be considered in the percentages	
	• for quantitative data: use of mean, standard deviation, median, 25th and 75th percentiles (interquartile range IQR), minimum and maximum and number of non-missing cases (95% confidence intervals for parameters of interest).	
	Adherence study:	
	Appropriate methods to deal with matched samples will be used. Suitable methods are Conditional Logistic Regression, Generalized Linear Mixed Models (GLMM) and Marginal Models (MM) with Gaussian or Logistic links.	
	Prescription errors sub-study:	
	The number of errors per hospitalization will be modeled with Generalized Linear Models (GLM). If significant correlation between hospitalizations from the same subject/hospital is found, then appropriate methods to address such data structure will be used. Suitable methods are GLMM and MM.	
	For both the main study and the sub-study:	
	Missing data will not be imputed.	
	In case of parametric procedures the underlying statistical assumptions, such as normality, will be checked. In case of severe violations of assumptions, transformations will be attempted as appropriate, and nonparametric methods may be used instead.	
	Exploratory post-hoc subgroup analyses may be performed if appropriate. All statistical tests will be two-tailed considering a significance level of 5%. Matching will be done using a propensity score approach on a variable ratio. The propensity score will be obtained using baseline and other retrospective information excluding	

any massing of adhering (outcome). The probability (propagaty) to
any measures of adherence (outcome). The probability (propensity) to
be in the STR group will be computed using logistic regression and
the cohorts matched using nearest neighbor (NN) matching algorithm
{27765} {27775}.

This study will be conducted in accordance with the guidelines of Good Pharmacoepidemiology Practices (GPPs) and Heads of Medicines Agencies (HMA) Good Pharmacovigilance Practices (GVP) including archiving of essential documents.

5. **AMENDMENTS AND UPDATES**

Amendment or Update Number	Date	Section of Study Protocol	Amendment or Update	Reason
<1>	[DD Month YYYY]	[Enter Text]	[Enter Text]	[Enter Text]

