9.3. Subject Selection

Adherence study

For each included subject, data will be collected for all patient-regimens lasting for at least 90 days during the observation period, that either include Stribild or are EACS v7.0 recommended, once daily regimens containing two NRTI plus one NNRTI or two NRTI plus one PI/r. Two cohorts will be considered: (i) STR and (ii) non-STR (Figure 1).

Figure 1. Study Scheme of Adherence study.

Legend: \bigstar start of patient-regimen; \blacksquare end of patient-regimen; i) STR; ii) non-STR.

STR and non-STR subjects are defined, for administrative purposes, according to the type of regimen they were receiving on 31st December 2013. Note that these STR and non-STR groups of subjects are defined only for subject selection purposes. Once subjects are selected, the

relevant unit of analysis is a patient-regimen and both matching and the statistical analysis will be performed at the patient-regimen level.

A single subject may contribute to the analysis with 1 or more patient-regimens. Moreover, a subject selected as part of the STR group (because he was on STR on 31st December 2013) may contribute in the analysis for both the STR and the non-STR group as the example of subject Z or W, in Figure 1 above.

Data will be collected on patient-regimens that were ongoing between 1st January 2009 and 31st December 2013, this is the observation period, and subjects must have had at least one pharmacy refill in 2013. All patient-regimens must have started before 30th September 2013 to ensure a minimum duration of at least 90 days, as determined in the inclusion criteria. Although patient-regimens may have been started before the beginning of the observation period and may still be in progress at the end of this period, for the purposes of this study, generally only data from the observation period shall be collected. The data collection period is the time during which the centers will enroll eligible subjects and enter the data onto the eCRF.

The patient-regimen selection for the adherence study will involve the following steps, to be initiated as soon as hospital approval has been granted at each site:

- 1. Search in Pharmacy's electronic records the pharmacist will search the pharmacy electronic database in order to identify all patients who have at least one ART refill in 2013.
- 2. Separate these patients into two cohorts according to the regimen they were receiving on December 31st 2013 (STR cohort and non-STR cohort)

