The subjects to be selected are the first ones from each sorted list of the random numbers. For example, if 80 subjects are to be selected in the STR cohort, the top 80 in the list are to be included.

For the selected subjects, check Inclusion and Exclusion criteria. If one subject does not meet the criteria, replace that subject with the next on the list (subject 81 in the example above). Repeat as necessary replacing each subject which does not meet the criteria by the next in the list. The same procedure should be followed if a subject meets the criteria but does not sign the informed consent.

Note that subjects are being selected instead of patient-regimens, so it is not obvious how many patient-regimens will be included. Nonetheless, considering that an average of 1.5 regimens in a 5 year period is likely to occur, then the 700 STR subjects and the 805 non-STR subjects will yield more than enough patient-regimens to reach the required patient-regimen sample size.

A Propensity Score Matching (PSM) approach will be applied subsequently on the merged dataset from all sites in order to maximize homogeneity between cohorts and reduce the impact of treatment-selection bias. A variable ratio between cohorts will be considered, so that 700 STR subjects are selected as cases and 805 non-STR as controls. The propensity score is defined as a subject's probability of receiving a specific treatment (STR) conditional on the observed covariates {27771}. When propensity scores are used in matching, treatment effects are unbiased when treatment assignment is strongly ignorable {27756}. On the other hand, treatment assignment is strongly ignorable if treatment cohorts and the outcome variable are conditionally independent given the covariates. This independence assumption will not hold in situations where there are variables not included as propensity score covariates that are correlated with outcome events and time dependent treatment selection {27757}.

The PSM procedure will include 4 steps:

- 1. Model choice: The propensity score will be computed using binary regression with a logit or a probit link function, depending on model fitting statistics. Statistical based criteria will be used to specify the covariates, such as the degree of association with STR odds.

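### Regimens are matched one by one, but the failure count is fixed at 1 January 2009 and the propensity score bars adherence on an earlier regimen, so later regimens may be confounded by prior adherence

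*Protocol*

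**What the plan says.** **Unit.** Protocol Section 9.3 states that the "relevant unit of analysis is a patient-regimen and both matching and the statistical analysis will be performed at the patient-regimen level". A subject selected for one cohort "may contribute in the analysis for both the STR and the non-STR group".

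**Failure history.** Table 2 in Section 9.4 lists the number of virological failures among the subject-level baseline characteristics, counted once: "has been achieved in that regimen) as of January 1st 2009". The next block of the same table is headed "characteristics to be evaluated at each" valid regimen initiation. Its dating rule is the day of initiation, or 1 January 2009 if the regimen was already running then. That block holds substance use, opioid substitution, mental disorder, AIDS status, hepatitis C and the Charlson index. The failure count is not in it.

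**Propensity score.** The Synopsis (Data Analysis) says the score is "obtained using baseline and other retrospective information excluding" "any measures of adherence (outcome", where the bracket contains only that last word. No exception is made for adherence on an earlier regimen.

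**Adjustment set.** The Synopsis (Variables) says: "All variables collected will be considered as confounders except the dependent or related dependent variable in question for each endpoint".

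**The protocol's own caveat.** Section 9.3 says the independence assumption behind the matching fails where there are "variables not included as propensity score covariates that are correlated with outcome events and time dependent treatment selection".

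**The concern.** When the unit is a regimen, pre-treatment means before that regimen started. For a subject's second regimen, adherence on the first is pre-treatment information. It is not the outcome of the second regimen. It plausibly influences both which regimen comes next and how well that regimen is taken, which makes it the kind of variable the caveat in Section 9.3 describes. As worded, the exclusion removes it from the score together with the outcome it was meant to remove.

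The failure count has a related, milder fault. For a regimen begun in 2012 the listed covariate describes the subject three years earlier, while smoking and comorbidity are brought up to the regimen's start.

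The STR versus non-STR odds of adherence above 90%, the primary endpoint, are at stake. If well-adhering patients are preferentially simplified to an STR, the STR is credited with adherence they already had. If STRs go preferentially to poor adherers, a real benefit is masked.

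**Working it through.** The protocol gives no figure for this bias, so there is none to reproduce. What can be reproduced is the adherence level used as an input. The selection and persistence values are my assumptions, shown as a range.

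**Inputs from the protocol**
- Section 9.6: mean adherence 97% (non-STR) and 98% (STR), SD 11%, cut at 90%. With a normal distribution, Φ(7/11) = 0.738 and Φ(8/11) = 0.766, which match the stated 0.74 and 0.77.
- Section 9.6: target difference 0.02.
- Section 9.3: 1.5 regimens per subject, 700 + 805 = 1,505 subjects.

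**Share of later regimens.** 1,505 × 1.5 = 2,257.5 regimens, of which 1,505 are a subject's first valid one. The rest are 752.5 / 2,257.5 = 0.5 / 1.5 = one third.

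**Bias formula.** Let A1 and A2 be adherence above 90% on the earlier and later regimen, with P(A1) = 0.74 and no true STR effect. If A1 is omitted, the spurious risk difference among later regimens is

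[P(A1 | STR) − P(A1 | non-STR)] × [P(A2 | A1 = yes) − P(A2 | A1 = no)].

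The first bracket follows from STR uptake u1 in prior adherers and u0 in prior non-adherers:
- P(A1 | STR) = 0.74·u1 / (0.74·u1 + 0.26·u0)
- P(A1 | non-STR) = 0.74(1 − u1) / [0.74(1 − u1) + 0.26(1 − u0)]

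Example with u1 = 0.50, u0 = 0.40: 0.370/0.474 − 0.370/0.526 = 0.781 − 0.703 = 0.077. With a persistence (second bracket) of 0.3, the bias is 0.023 among later regimens and 0.023/3 = 0.008 over all regimens.

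| u1 vs u0 (assumed) | Imbalance in A1 | Bias, later regimens (persistence 0.2 to 0.5) | Bias, all regimens (÷ 3) |
|---|---|---|---|
| 0.50 vs 0.45 | +0.039 | +0.008 to +0.019 | +0.003 to +0.006 |
| 0.50 vs 0.40 | +0.077 | +0.015 to +0.039 | +0.005 to +0.013 |
| 0.50 vs 0.30 | +0.156 | +0.031 to +0.078 | +0.010 to +0.026 |
| 0.40 vs 0.50 | −0.079 | −0.016 to −0.039 | −0.005 to −0.013 |
| 0.30 vs 0.50 | −0.169 | −0.034 to −0.084 | −0.011 to −0.028 |

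Dividing by three assumes that first regimens carry no such bias and that matching keeps the same mix of first and later regimens.

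**An upper bound on persistence from the protocol.** Section 9.6 assumes that patients adherent on non-STR are also adherent on STR. Then P(adherent on STR | not adherent on non-STR) = (0.77 − 0.74)/0.26 = 0.115, and persistence is 1 − 0.115 = 0.885. A 7-point imbalance in A1 then gives 0.07 × 0.885 = 0.062 among later regimens and 0.021 overall. This is an extreme sizing assumption for a non-STR to STR change, so I treat it as a ceiling.

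**Failure count.** No arithmetic is needed. The fixed date is right for a regimen already running on 1 January 2009 and out of date for any regimen begun later, including a subject's first valid one.

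**The case against.** The strongest reply has four parts.

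1. **The failure history is not lost.** A reader might infer that failures in 2009–2013 are ignored. The documents do not support that. Table 2 collects every dated HIV RNA and CD4 test in the observation period, the score may use other retrospective information, and collected variables other than the dependent or related one count as confounders. Later failures can be derived and are not barred for the primary endpoint. This stands: the fault is a covariate listed at the wrong date.

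2. **The exclusion may mean only the outcome.** The bracketed word suggests that the index regimen's adherence was the target, and keeping that out of the score is correct. But the text says any measure and exempts nothing. The related-variable clause in the adjustment rule can be read the same way. An analysis that follows the wording omits prior adherence, so this reply argues for clarification and does not remove the fault.

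3. **Other terms reduce the bias.** Substance use, mental disorder, AIDS status and comorbidity are updated at each regimen's start. The imbalance that matters is what remains after matching on these, which may be smaller than the table assumes. This stands. Section 9.8 also accounts for the panel structure, but that deals with correlation within subjects and does not by itself remove confounding by prior course.

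4. **The limitation is disclosed.** Sections 9.3 and 9.10 acknowledge the independence assumption and residual selection bias. That does not justify barring a measured covariate.

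A reader might also infer that every later STR versus non-STR comparison is confounded, or that the primary question goes unanswered for switchers. Neither follows. Confounding depends on selection that the documents do not quantify, and the becoming-unsuppressed endpoint is restricted to regimens starting at HIV RNA ≤50 copies/mL.

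**Conclusion.** The point holds in a limited form. Two stated rules do not fit the patient-regimen unit. One leaves out of the score a plausible pre-treatment confounder for about one third of regimens, and the other uses a failure count that is out of date for regimens begun after 1 January 2009.

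The direction of any bias is unknown. Among later regimens, moderate selection (uptake differing by 10 points, persistence 0.3) already gives about 0.023 in absolute size, above the 0.02 the study is sized to detect. Over all regimens the assumed range is −0.028 to +0.026, and 0.02 is reached only under strong selection or strong persistence. These sizes rest on assumed uptake and persistence, on no other covariate absorbing the imbalance, and on the protocol's 1.5 regimens per subject. They show that the bias could matter, not that it will occur. The correction is cheap and should be made before the propensity model is fixed.

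**What to change.** 1. **Table 2, failure count.** Apply the dating rule already used in the next block: the day of regimen initiation, or 1 January 2009 if the regimen started earlier. Derive 2009–2013 failures from the HIV RNA tests already collected. Because the failure definition is tied to a regimen, state how tests taken between valid regimens are handled.
2. **Synopsis, Data Analysis and Variables.** Limit the propensity-score exclusion, and the related-variable exclusion, to adherence during the regimen being analysed.
3. **Propensity score.** For later regimens, add regimen order and adherence on the immediately preceding valid regimen. Use a category for no prior valid regimen, so that the rule against imputing missing data drops no regimen.
4. **Sensitivity analysis.** Repeat the primary analysis on one regimen per subject, the first valid one. This is preferable to exact matching on regimen order, which would use up pairs from the planned 1,030 and still leave pre-2009 history unmeasured.

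**Cost.** Wording and derivation, with no new data collection. Refills are collected only for valid regimens, so prior adherence is unknown where the preceding regimen was not valid, and some residual confounding remains. Overall inadequate adherence includes selective adherence only for non-STR regimens, so the report should say which prior-adherence measure is used. The sensitivity analysis uses about two thirds of the regimens and is correspondingly less precise.
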